## 9.9. Safety Evaluations

Safety assessments will be performed during the screening and double-blind treatment phase as specified in the Time and Events Schedule. Safety assessments will include, but are not limited to, AEs, laboratory measures (hematology and clinical chemistry), vital signs, ECG, physical and neurological examinations, dermatological examination, MRI (see Section 9.4.2.3), suicidality risk as assessed by C-SSRS (see Section 9.5.8), and evaluation of well-being (see Section 9.5.7).

### 9.9.1. Adverse Events

Adverse events, including AESIs, reported by the subject (or, when appropriate, by a study informant, partner, caregiver, or the subject's legally acceptable representative) will be monitored for the duration of the study, as specified in Section 12.

### 9.9.2. Vital Signs

Vital signs (body temperature, pulse rate, blood pressure) will be collected at the time points indicated in the Time and Events Schedule. Blood pressure and pulse rate measurements will be assessed supine and standing with a completely automated device. Manual techniques will be used only if an automated device is not available. Blood pressure and pulse rate measurements should be preceded by at least 5 minutes of rest in a quiet setting without distractions (eg, television, cell phones).

### 9.9.3. Electrocardiogram

Twelve-lead ECGs will be collected at the time points listed in the Time and Events Schedule, and at all time points will be recorded 1 to 4 hours after administration of study drug. During the collection of ECGs, subjects should be in a quiet setting without distractions (eg, television, cell phones). Subjects should rest in a supine position for at least 5 minutes before ECG collection and should refrain from talking or moving arms or legs. For those subjects with PK sampling during the same interval, the ECG should be performed close to the collection of the PK sample (ie, both ECG and PK within a 20 minute window).

At all time points, triplicate ECGs are required, ie, 3 individual ECG tracings should be obtained as closely as possible in succession, but no more than 2 minutes apart. The full set of triplicate recordings should be completed in less than 4 minutes.

During the study, the clinical investigator will review the ECG for immediate management and to mark abnormalities. A description of the overall assessment (ie, normal or abnormal plus reason) will be made and a copy of the trace will be placed with the source data. All ECGs will additionally be transmitted to be read and interpreted by a central reader appointed by the sponsor.

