### **SAFETY EVALUATIONS**

The safety of atabecestat in the study population will be assessed by monitoring AEs and concomitant medication use; safety laboratory testing (hematology, chemistry, urinalysis); triplicate recording of 12-lead electrocardiograms (ECG) at baseline and at 1 to 4 hours after dosing during the double-blind treatment phase; measurement of vital signs (blood pressure, pulse rate, temperature) and body weight; MRI imaging; and physical, neurological, and dermatological examinations. In addition, suicidality risk will be evaluated using the Columbia Suicide Severity Rating Scale (C-SSRS). Subjects will also complete the Assessment of Psychological Well Being questionnaire.

An independent external Data Monitoring Committee (DMC) will be established to monitor study data on an ongoing basis to ensure the continuing safety of the subjects enrolled in this study.

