- j Serves as baseline assessment and will be performed between Day -10 and Day -5 and at least 2 days after the amyloid disclosure visit.
- k At selected centers only.
- l Amyloid PET imaging or lumbar puncture to collect a CSF sample for determination of A $\beta$ 1-42 levels, or both, will be performed to assess elevated amyloid accumulation at study entry and to determine eligibility. Elevated amyloid accumulation can be determined by results for either of these biomarker evaluations, but the decision on which tests are going to be done must be made before either result is available. The amyloid disclosure visit will be performed when both results, if applicable, are available.
- m Only at sites capable of processing PBMC samples.
- n MRI and PET collection can be performed at the same visit based on-site preference, and results must be available during screening phase to confirm subject eligibility.
- o For safety; both volumetric and task-free functional MRI.
- p No subjects will receive more than 3 amyloid PET scans during the study.

Phase	Double-blind Treatment Phase																												Early Termination	Follow up Visit c	
	Month (M) a	M0 (D1)	W2*	M 1	M1 +2W	M 2	M2 +2W	M 3	M 4	M 5	M 6	M 8	M 9	M 10	M 12	M 15	M 18	M 21	M 24	M 27	M 30	M 33	M 36	M 39	M 42	M 45	M 48	M 51			M 54
Visit Window (± days)	0	± 2	± 4	± 2	± 4	± 2	± 12	± 12	± 12	± 12	± 12	± 12	± 12	± 12	± 12	± 12	± 12	± 12	± 12	± 12	± 12	± 12	± 12	± 12	± 12	± 12	± 12	± 12	± 12		
Visit Number	7	8	9	10	11	12	13	14	15	16	17	18	19	20	21	22	23	24	25	26	27	28	29	30	31	32	33	34		35	
Study Procedures																															
Vital signs (supine and standing blood pressure, pulse)	X d						X			X		X		X		X		X		X		X		X		X		X	X	X	
Triplicate 12-lead ECG i	X d		X				X			X				X		X		X		X		X		X		X		X	X	X f	
Height																												X	X		
Weight	X d									X				X		X		X		X		X		X		X		X	X	X	
Temperature	X d						X			X		X		X		X		X		X		X		X		X		X	X	X f	
Assessment of Psychological Well Being	X						X					X			X		X		X		X		X		X		X	X	X	X	
C-SSRS (since last visit)	X d	X	X	X	X	X	X	X	X	X	X	X	X	X	X	X	X	X	X	X	X	X	X	X	X	X	X	X	X	X	X
Clinical Laboratory Assessments																															
Hematology and chemistry	X	X	X	X	X	X	X	X	X	X	X	X	X	X	X	X	X	X	X	X	X	X	X	X	X	X	X	X	X	X	X f

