g Whenever a skin lesion not previously documented is reported by the subject or the investigator, in addition to a dermatological exam performed by a dermatologist (as defined in Section 9.1.2), digital images of the lesion will be acquired at the time (taken by dermatologist or assigned designee) the lesion is discovered and at follow-up visits with a frequency that is deemed appropriate by the sponsor of the study. Duration of follow-up of newly documented skin lesions or depigmentation might extend beyond the treatment period, as judged adequate by the sponsor to ensure the safety of subjects in this study.

h To be done at Early Termination visit only if not performed at Month 12. Note: If a subject discontinues study treatment before completion of the double-blind treatment phase or is withdrawn during the double-blind treatment phase, the subject will be asked to complete this at the Early Termination visit if early termination is before Month 12.

- i Triplicate ECG recordings to be obtained 1 to 4 hours postdose. The 3 individual ECG tracings are to be obtained as close as possible in succession, but no more than 2 minutes apart, and the full set of triplicate recordings are to be completed in less than 4 minutes.
- j Must be performed prior to lumbar puncture.
- k Only if assessment not performed during previous visit as scheduled (eg, for PACC and RBANS, perform assessment that was not performed at the last visit per the alternating pattern of these assessments).
- l At selected centers only.
- m Blood samples for plasma PK determinations will be collected predose and between 1 to 4 hours postdose.
- n CSF collection should be done after all other assessments (eg, safety, cognitive, functional, clinical, medical resource utilization/health outcomes).
- o May be collected during the screening period upon confirmation of eligibility based on the Steps I to IV screening assessments.
- p Flexible CSF time point which may be rescheduled to any time point during the double-blind treatment phase, following interim review of the biomarker data.
- q In subjects who experience significant increase in hepatic enzymes, an additional blood draw may be drawn in an optional immunologic substudy (see Section 3.2.6.2).

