#### Pharmacokinetics, Metabolism, and Pharmacodynamics

Multiple dose pharmacokinetic results from Study 54861911ALZ1002 showed steady-state drug plasma levels were reached by Day 5, steady-state plasma  $C_{\max}$  and area under the concentration-time curve from 0 to tau hours postdosing ( $AUC_{\tau}$ ) were approximately dose proportional across the doses studied, and median time to maximum plasma concentration ( $t_{\max}$ ) was 2 to 4 hours. On Day 14, the mean terminal (apparent elimination) half-life ( $t_{1/2}$ ) ranged from 14.4 to 18.5 hours across doses, and mean accumulation ratios for steady-state  $C_{\max}$  and  $AUC_{\tau}$  ranged from 1.27 to 1.73 and 1.34 to 2.17, respectively.

Only minor metabolites were observed in human plasma from Study 54861911ALZ1002, and none of them were human specific. In Studies 54861911ALZ1001 and 54861911ALZ1002, the area under the plasma concentration curve (AUC) ratio of DIAT metabolite to parent compound was below 10% and the  $C_{\max}$  ratio of DIAT metabolite to parent compound ranged from 4% to 7%. Other metabolites identified in human plasma showed lower exposure.

For assessable doses in Study 54861911ALZ1001, atabecestat plasma exposure was similar between males and females, with male:female ratios for  $C_{\max}$  of 0.987 and 0.820, and for area

under the plasma concentration curve observed from administration to the last measurable concentration ( $AUC_{last}$ ) of 0.814 and 0.667 for the 30- and 150-mg dose groups, respectively.

Study 54861911ALZ1003 showed food had little effect on exposure to a atabecestat tablet formulation following a high fat/high calorie meal. In the fed state, median  $t_{max}$  was delayed by 1.5 hours compared to the fasted state.

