10. Subject has a history within the past 2 years or current diagnosis of significant psychiatric illness, per the most current version of the Diagnostic and Statistical Manual of Mental Disorders (DSM) (including but not limited to major depressive disorders and anxiety disorders) (subjects who are symptom free or with minimal limited symptoms may be included); or the subject has a current diagnosis or history of schizophrenia or bipolar disorder.
11. Subject has a relevant history of or current neurological disease other than preclinical AD, which may make interpretation of possible new neurological signs or symptoms difficult.
12. Subject has had a history within the last 5 years of a serious infectious disease affecting the brain (including neurosyphilis, meningitis, or encephalitis) or head trauma resulting in protracted loss of consciousness.
13. Subject has a history of epilepsy. Subject has a history of fits or unexplained black-outs other than vasovagal syncope within 10 years before screening.

14. Criterion modified per Amendment 5
  - 14.1 Subject has a hypopigmentation abnormality of the skin such as vitiligo at screening dermatological exam. Small localized lesions other than vitiligo are allowed.
15. Subject has any amyloid-related imaging abnormalities – edema or effusion (ARIA-E) at screening.
16. Subject has a clinically significant abnormal physical or neurological examination or vital signs at screening or baseline (Day 1 predose), which in the opinion of the investigator is not appropriate and reasonable for the population under study.
17. Criterion modified per Amendment 5
  - 17.1 Subject has, in the opinion of the investigator, a clinically significant 12-lead ECG abnormality (including left bundle branch block, atrioventricular [AV] block of second degree or higher, permanent pacemaker or implantable cardioverter defibrillator) at screening or baseline (Day 1 predose). The screening QTcF must be evaluated and must not exceed 450 msec in males or 470 msec in females. For triplicate ECGs, 2 of the 3 tracings must be below 450 msec in males or 470 msec in females. ECG recordings may be repeated once, and in the case of a question, a cardiologist and sponsor medical monitor should be consulted.

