Medical resource utilization and health outcomes will be explored with the HRUQ, SF-36, and EQ-5D-5L (see Section 9.8).

Safety (ECG, vital signs, safety labs, MRI, physical, neurological and dermatologic examination, and C-SSRS), and tolerability (AEs and Assessment of Psychological Well Being) will be assessed at regular intervals during the double-blind treatment phase, as listed per the Time and Events Schedule, and described in Sections 9.5.7, 9.5.8, and 9.9). Most of these safety assessments (except for the MRI, ECG, and Assessment of Psychological Well Being) will be done predose at the specified visit. Questionnaires assessing a subject's concern about AD and his/her perception of future time will be repeated at regular intervals during the double-blind treatment phase as indicated on the Time and Events Schedule (see also Sections 9.5.4 and 9.5.6). A comprehensive skin examination by a dermatologist will be repeated at Month 12 of the double-blind treatment phase, or at the Early Termination (ET) visit for any subject who withdraws from the study prior to Month 12.

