2.3. Reference Start Date and Analysis Phases

The analysis reference start date (Study Day 1) is defined as the date of the first dose of study medication. The Study Day of an event start or stop date is defined relative to the analysis reference start date as:

- Event date – analysis reference start date + 1, if the visit/event date is on or after the analysis reference start date, or

- Event date – analysis reference start date -1, if the visit/event date is before the analysis reference start date

Study Days <1 will be considered in the Screening analysis phase; Study Days \geq 1 (there is no Study Day 0) will be considered in the Double-blind analysis phase.

For visit dates prior to, or on, the date of the last dose of study medication, an Analysis Day will be defined as above relative to the analysis reference start date. For visit dates after the treatment end date, an Analysis Day is defined relative to the treatment end date as: Visit date – treatment end date + 1.

- Analysis reference start date (date of first dose as above) for all timepoints after first dose (whether before or after last dose)
- For assessments after last dose, use last observation before last dose as the reference time point.

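### Protocol 9.9.3 times every ECG after dosing while other sections make the Day 1 ECG predose, and SAP 2.4 has no predose condition on baseline, so a post-dose Day 1 ECG could become a subject's QTc baseline

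*Protocol*

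**What the plan says.** Three Protocol statements point to post-dose recording, or at least do not require predose recording.

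- Section 9.9.3: ECGs "at all time points will be recorded 1 to 4 hours after administration of study drug". Day 1 is not excepted.
- Time and Events Schedule, footnote i, attached to the title of the ECG row and so to every visit in it: "Triplicate ECG recordings to be obtained 1 to 4 hours postdose".
- Section 9.1.3: most safety assessments, "except for the MRI, ECG, and Assessment of Psychological Well Being) will be done predose at the specified visit". This takes ECGs out of the general predose rule.

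Three others set the baseline ECG before dosing or apart from the post-dose recordings.

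- The Day 1 cell of the same ECG row carries footnote d, which means predose.
- Exclusion criterion 17.1 considers ECG abnormalities "at screening or baseline (Day 1 predose").
- The synopsis lists ECGs "at baseline and at 1 to 4 hours after dosing during the double-blind treatment phase", which separates baseline from the post-dose recordings.

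On the analysis side, SAP 2.3 states: "The analysis reference start date (Study Day 1) is defined as the date of the first dose of study medication". That is a date without a clock time. In SAP 2.4, Table 1, the baseline window is Days -120 to 1 with target Day 1, the visit closest to target is used, and the next window opens on Day 2. SAP 6.3 lists an ECG at randomization without saying predose, and takes the value on a date as the average of the triplicate. It reports mean change from baseline, QTc change categories with cut-offs at 30 and 60 msec, and a listing that includes changes above 30 msec.

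**The concern.** QT prolongation is one of the potential risks named in Protocol 1.5, and the 1 to 4 hour window was chosen because QTc changes were most marked then in the thorough QT study. A baseline ECG taken in that window on Day 1 already contains part of the drug effect. Subtracting it from later on-treatment values, which are taken in the same window, shrinks the change in active-arm subjects and leaves placebo subjects untouched.

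The SAP rules would let such a value through. A Day 1 record is closer to target than a screening record, so it wins the baseline slot. It cannot fall into a post-baseline window, because none includes Day 1. SAP 6.3 does restrict the regression behind the linear-derived QTc to observations before treatment began, and SAP 7.1 states that the randomization PK sample is pre-dose. No similar condition is set for the ECG baseline.

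**Working it through.** The plan states no figure for this, so there is none to reproduce. The check estimates how much of the steady-state effect a post-dose Day 1 ECG would already carry.

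**Inputs**

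- Protocol 1.4, pharmacokinetics: "mean accumulation ratios for steady-state" Cmax of 1.27 to 1.73 and AUC of 1.34 to 2.17; terminal half-life 14.4 to 18.5 hours.
- Protocol 1.4, safety: largest mean QTc difference from placebo on Day 7 of 6.6 msec at 50 mg (90% CI 4.02 to 9.12) and 15.5 msec at 150 mg.
- Protocol 3.2.3: modelled QTcF change at 25 mg expected to stay clearly under 5 msec.

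**Assumption:** the QTc effect is proportional to plasma concentration. The Day 1 share of the steady-state effect is then 1/R, where R is the accumulation ratio.

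**Share lost in one affected subject**

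- Cmax: 1/1.73 = 0.58 and 1/1.27 = 0.79. Lost: 58% to 79%. Still visible: 21% to 42%.
- Half-life check: R = 1/(1 − exp(−24 ln 2 / t½)) gives 1.46 at 14.4 h and 1.69 at 18.5 h, so 59% to 69% lost. This agrees with the stated ratios.
- AUC ratios instead: 1/2.17 = 0.46 to 1/1.34 = 0.75. Cmax suits a 1 to 4 hour window better.

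**In milliseconds at 25 mg**

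- Scaling by dose: 6.6 × 25/50 = 3.3 msec, in line with the modelled expectation.
- Lost: 3.3 × 0.58 = 1.9 to 3.3 × 0.79 = 2.6 msec. Visible: about 1.4 down to 0.7 msec.
- Carrying the 90% CI: (4.02/2) × 0.58 = 1.2 to (9.12/2) × 0.79 = 3.6 msec.

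**Sensitivity to the shape of the curve** (fitted through 6.6 and 15.5 msec, with dose standing in for concentration)

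- Power curve: exponent ln(15.5/6.6)/ln 3 = 0.78. Effect at 25 mg is 3.9 msec; 65% to 83% lost, or 2.5 to 3.2 msec.
- Straight line with intercept: slope (15.5 − 6.6)/100 = 0.089, intercept 2.15. Effect at 25 mg is 4.4 msec; 79% to 89% lost, or 3.4 to 3.9 msec. This line implies a non-zero effect at zero dose, so it is an outer bound.

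**At group level.** If a share f of a dose group has a post-dose baseline, the mean change is reduced by f × 58% to f × 79%:

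| f | reduction in group mean change |
|---|---|
| 25% | 14% to 20% |
| 50% | 29% to 39% |
| 100% | 58% to 79% |

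Losing half of the group mean would need f of 0.5 × 1.27 = 64% to 0.5 × 1.73 = 87%. No document gives f.

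**The case against.** The strongest reply is that the schedule already controls Day 1. The Day 1 cell is marked predose, and footnote e allows the first dose only once the predose assessments are complete. Criterion 17.1 uses the Day 1 predose ECG for eligibility, and Section 9.1.3 puts the eligibility review before randomization. Section 9.9.3 cannot be literal for every ECG, because the schedule includes a screening ECG before any drug and, in some subjects, a follow-up ECG 7 to 28 days after the last dose. Day 1 PK sampling is also predose only, so no post-dose sample exists that day to pair with an ECG. This stands, and it makes predose recording the likely practice. It does not remove the conflicting text or supply the missing SAP condition.

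A reader might infer three stronger things that the documents do not support.

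- That most of the trial's QTc effect would be hidden. The 58% to 79% applies only to a subject whose Day 1 ECG was post-dose. The accumulation ratios also come from a study of 5 to 150 mg in healthy elderly subjects and are not specific to 25 mg.
- That SAP 6.3 pools predose and post-dose tracings from Day 1. It describes averaging one triplicate set completed within 4 minutes. Pooling of separate sets is not clearly prescribed.
- That the discontinuation criterion for an increase above 60 msec in Protocol 10.2 is governed by the SAP window. It is applied during conduct, in consultation with the medical monitor, and nothing links it to SAP 2.4.

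**Conclusion.** The Protocol contradicts itself on the timing of the Day 1 ECG, even within one row of the schedule, and the SAP baseline rule would accept a post-dose value ahead of a clean screening value. Where that happened in an active-arm subject, QTc change from baseline is biased towards zero by 58% to 79% of the steady-state effect, or about 2 to 3 msec at 25 mg. This assumes an effect proportional to concentration and a Day 1 recording near the first-dose peak; the other curve shapes tried reach 3.9 msec. A subject with a larger effect than average would lose more in milliseconds.

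The outputs exposed are those based on change from baseline, chiefly the mean change. A shift of this size would seldom move a subject across the 30 or 60 msec cut-offs; Protocol 1.5 reports no increase above 30 msec even at 50 mg. Categories of absolute QTc are unaffected. The effect on a dose group cannot be stated, because the share of affected subjects is unknown and may be small. The case for acting is that the expected signal is itself only a few milliseconds and the correction is cheap.

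**What to change.** 1. Reconcile Protocol 9.9.3, footnote i and the ECG wording in 9.1.3 with footnote d in the Day 1 cell, criterion 17.1 and the synopsis. Dosing has stopped, so this now serves mainly to document which timing applied.
2. Add to SAP 2.4 or 6.3 that the ECG baseline is the last triplicate recorded before the first dose, or the screening triplicate if there is no Day 1 predose set, and that a Day 1 post-dose triplicate is not used as baseline.
3. Before the QTc tables are run, compare the Day 1 ECG time with the first-dose time and report, by treatment group, how many subjects had a post-dose Day 1 recording. That supplies the missing share f.

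The cost is one SAP sentence and one programmed check. Protocol 9.1.1 requires assessment times to be recorded, and 9.6.1 requires the dose time at the visit. Both allow these to sit in source documents or on the requisition form instead of the eCRF, so some times may have to be retrieved. Where the order cannot be established, the SAP should say whether the screening value is used.

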### 9.9.4. Physical and Neurological Examinations

The study investigator, or other authorized and appropriately qualified designee, will perform the physical and neurological examinations at the time points listed in the Time and Events Schedule.

Any clinically relevant changes occurring during the study must be recorded on the AE section of the eCRF. Any clinically significant abnormalities persisting at the end of the study or early withdrawal will be followed by the investigator until resolution or until a clinically stable endpoint is reached.

Height and body weight will be measured per the Time and Events schedule.

#### **9.9.5. Dermatological Examination**

All subjects will undergo a comprehensive skin examination performed by a dermatologist (as defined in Section 9.1.2) during screening and again at Month 12 (or at the ET visit if subject withdraws from study or discontinues treatment prior to Month 12 assessment) to exclude the presence of skin lesions or depigmentation. A digital photograph of the frontal scalp, open eyes, and eyebrows will be collected by the dermatologist or a qualified designee to document changes noted by the dermatologist to monitor for dermatological safety. This is an essential requirement of the safety monitoring in the trial.

Whenever a skin lesion not previously documented is reported by the study subject, informant, investigator, or study personnel, and if deemed medically relevant, subject should undergo a dermatologic exam by a dermatologist. In addition digital images of the lesion will be acquired by the dermatologist or qualified designee at the time the lesion is discovered and at follow-up visits with a frequency which is deemed appropriate by the sponsor. As skin lesions may be temporary, the site personnel may consider documenting immediately at the site with a photograph in addition to referring the subject to the dermatologist. Duration of follow-up of newly documented skin lesions or depigmentation might extend beyond the double-blind treatment phase, as judged adequate by the sponsor to ensure the safety of participants in this study.

Lightening of hair and lightening of skin are AESIs in this study based on nonclinical studies conducted with atabecestat or reported findings for BACE knockout animals or other BACE inhibitors in development (see Section 12.3.1).

